### **Study Design:**

- Patients who have to receive Prostaglandin E1 treatment due to congenital heart disease followed in the neonatal department of our hospital will be included in the study after their consent and approval with their families without recording their identity information.

- Pyloric thicknesses will be measured by a pediatric radiologist once a week (at least twice) during the period when patients use PGE1.
- After reaching the sufficient number of cases (20 cases), increases in the pyloric wall thickness dimensions will be compared with statistical analysis. The number of cases was determined in accordance with the rate of hospitalization in our unit during the determined period (18 months). In this way, since the studies are in the form of a case report and the original article cannot be found in the literature, the observed power of the study will be calculated after the study is completed.

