# **EFFECT OF PROSTAGLANDİN E1 TREATMENT ON PYLORİC WALL THİCKNESS İN NEWBORN PERİOD**

**DOCUMENT DATE: MAY 6, 2019**

## **Study Protocol:**

### **Effect of prostaglandin E1 treatment on pyloric wall thickness in newborn period**

Intravenous prostaglandin E1 infusion is referred to as ductus dependent diseases, in systemic (aortic blood flow) circulation (eg critical aortic coarctation, intermittent arcus aorta, hypoplastic left heart, transposition of great artery), or lung blood flow through patent ductus arteriosus ( For example, pulmonary valve atresia, tricuspid valve atresia, hypoplastic right heart) is a life-saving drug used to ensure that the duct remains open until a full, partial or temporary surgical correction or intervention is made. In the antenatal period, the placenta is a good source of prostaglandins. However, with the disappearance of the placental circulation after birth, many mechanisms ensure that the patent ductus arteriosus closes first functional and then anatomically. Due to these mechanisms occurring in the early days of life, babies who have ductus-dependent congenital heart diseases show themselves with severe clinical signs and symptoms such as cyanosis and circulatory disorders in this early neonatal period, when ductus begins to close when diagnosis and treatment are not performed. Echocardiography should be performed by the pediatric cardiology specialist as soon as possible after delivery to babies diagnosed in the antenatal period, and if a ductus-dependent congenital heart disease diagnosis is confirmed, PGE1 infusion should be started immediately, and the patient should be consulted with a pediatric cardiovascular surgery specialist and a surgical intervention plan should be provided as soon as possible. Due to these mechanisms occurring in the early days of life, babies who have ductus-dependent congenital heart diseases show themselves with severe clinical signs and symptoms such as cyanosis and circulatory disorders in this early neonatal period, when ductus begins to close when diagnosis and treatment are not performed. Echocardiography should be performed by the pediatric cardiology specialist as soon as possible after delivery to babies diagnosed in the antenatal period, and if a ductus-dependent congenital heart disease diagnosis is confirmed, PGE1 infusion should be started immediately, and the patient should be consulted with a pediatric cardiovascular surgery specialist and a surgical intervention plan should be provided as soon as possible. Prostaglandin E1 infusion is given as a continuous intravenous infusion. PGE1 has some side effects. The most common side effects are apnea, hyperthermia, and vasodilatation on the skin, they occur around 10-14% and are usually dose-related side effects. In addition, bradycardia, hypotension, convulsion, tachycardia, diarrhea, sepsis, necrotizing enterocolitis, hypernatremia, hyponatremia,

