
hypokalemia, respiratory depression, arrhythmia, congestive heart failure, gastric regurgitation, bleeding, anuria, hematuria and hypoglycaemia are more rare effects. The frequency and severity of these side effects usually depend on the dose of the drug and the time used. Many of these side effects disappear or decrease significantly when the medication is stopped or the dose is reduced. An important complication that can be seen with long-term use is cortical hyperostosis in long bones. Among the very rare side effects of the drug Prostaglandin E1 are hyperplasia of the gastric mucosa and the development of pyloric stenosis. Hypertrophic pyloric stenosis develops as a result of hypertrophy of circular pyloric muscles in the newborn period. Ultrasonography (USG) is the primary diagnosis and imaging method, because it does not contain radiation, it has replaced contrast studies. In ultrasonography, the thickness of the pyloric muscle from the mucosa to the serosa is more than 2-3 mm and the length of the pyloric canal is over 16 mm. In the literature, there is no study on the effect of PGE1 increasing the pyloric wall thickness in newborns, there is a case report from our hospital in this regard. In this study, we aimed to evaluate the effects of the drug on pyloric wall thickness prospectively with weekly ultrasonography measurements in infants given PGE1 infusion due to congenital heart disease. Ultrasonography measurements will be made at the bedside (with the ultrasonography device of our unit) by an experienced pediatric radiologist in pediatric cases. No intervention in the treatment, medical decisions and follow-up of patients will be made. Neonatal babies who were born in Hacettepe University Faculty of Medicine Ihsan Dogramaci Children's Hospital Neonatal Intensive Care Unit and who were receiving prostaglandin E1 infusion due to PDA-dependent congenital heart disease will be included in the study. Infants who do not have consent to participate, babies with chromosomal disease and hereditary metabolic disease will not be included in the study. In addition, babies who have an exitus in the first week of life and whose ultrasonography measurements cannot be obtained, and babies whose prostaglandin E1 infusion is discontinued by taking the second ultrasonographic measurement in the first week of life will be excluded from the study.

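### The aim is the effect of PGE1, but with one treated group, every scan on the drug and none timed from infusion start, drug effect and newborn growth cannot be separated

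*Protocol*

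**What the plan says.** The aim, in the Study Protocol text, is causal: "we aimed to evaluate the effects of the drug on pyloric wall thickness prospectively with weekly ultrasonography measurements". Eligibility admits one kind of infant, those "who were receiving prostaglandin E1 infusion due to PDA-dependent congenital heart disease will be included in the study". No untreated group or set of age-specific normal values is named.

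The scan schedule is in the second bullet of Study Design: "Pyloric thicknesses will be measured by a pediatric radiologist once a week (at least twice) during the period when patients use PGE1". The third bullet gives the analysis: "increases in the pyloric wall thickness dimensions will be compared with statistical analysis", once 20 cases are reached.

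On exposure, the Study Protocol text says "Prostaglandin E1 infusion is given as a continuous intravenous infusion". For babies diagnosed antenatally it adds that "if a ductus-dependent congenital heart disease diagnosis is confirmed, PGE1 infusion should be started immediately". The only other statement on scan timing is an exclusion rule for infants whose infusion is "discontinued by taking the second ultrasonographic measurement in the first week of life will be excluded from the study". That rule counts from birth, not from the start of the infusion.

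**The concern.** There are two separate problems.

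First, a rise in thickness during the infusion could come from the drug, from normal newborn growth, or from both. The planned comparison of increases does not distinguish these, so it does not answer the question in the aim. A significant rise could be reported as a drug effect when growth alone produced it. The Protocol says there is no earlier study of this effect, only a case report from the same hospital, so such a result would have little to be set against.

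Second, no scan is anchored to infusion start. Time on drug at the first scan can differ between infants, and any change before that scan is not observed. The measured change therefore need not cover the same stretch of exposure in each infant.

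**Working it through.** **Inputs.** From the Protocol: one treated group, weekly scans (at least two) while on PGE1, continuous infusion, 20 cases. Assumed, because the Protocol gives none: a paired t-test, a two-sided 5% level, scans at days 0, 7 and 14 of infusion (days 0 and 7 in step 2), the spread of age at infusion start, and the growth between scans. The Protocol's only figure, 20 cases, rests on the unit's admissions over 18 months. The admission rate is not stated, so 20 cannot be re-derived and is used only as an input.

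**1. Within infants.** Write thickness as

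thickness = infant intercept + g × age + d × days on drug + error.

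If infant *i* starts the infusion at age s_i and every scan is on the drug, then age = s_i + days on drug. Between two scans Δ days apart, the expected change is (g + d) × Δ. Only the sum g + d can be estimated. As a matrix check, 20 infant intercepts + age + days on drug = 22 columns, and the rank is 21. The drug slope is not estimable within infants, whatever the growth rate.

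**2. Between infants.** Infants who start at different ages give some contrast. With scans at days 0 and 7, days on drug have variance 3.5² = 12.25. If age at start has SD s, the correlation of age with days on drug is √(12.25 / (12.25 + s²)):

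| s (days, assumed) | Correlation | Variance inflation, 1/(1 − r²) |
|---|---|---|
| 1 | 0.96 | 13.3 |
| 2 | 0.87 | 4.1 |
| 3 | 0.76 | 2.4 |

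This contrast is imprecise but not impossible. It compares different infants, so it is open to confounding by heart lesion and severity.

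**3. What growth alone could produce.** For n = 20, df = 19 and t(0.975) = 2.093, a mean rise is significant once it exceeds 2.093/√20 = 0.468 SD of the within-infant change, whatever its cause. With zero drug effect, the upper-tail rejection probability from the noncentral t distribution (noncentrality = growth × √20) is:

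| Growth between scans (SD of the change, assumed) | Chance of a significant increase |
|---|---|
| 0 | 2.5% |
| 0.25 | 18.5% |
| 0.5 | 56% |
| 0.75 | 89% |
| 1.0 | 99% |

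**4. First scan.** If the first scan falls u_i days after infusion start, the measured change covers u_i onwards and misses d × u_i under a linear effect. The Protocol does not fix u_i. The exclusion rule may imply an early first scan, but it refers to age.

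**The case against.** The case on the other side has real parts.

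- **Immediate start is background advice.** The sentence concerns antenatally diagnosed babies and is not a rule of this study. That is correct, but step 1 needs only an uninterrupted infusion and holds for any start age.
- **The two problems pull against each other.** If all infants start soon after birth, the first-week-of-life wording is close to an infusion anchor. If start ages vary, age and time on drug are not fully tied between infants. This has some force, and it is why non-estimability is claimed only within infants. It does not supply the missing anchor, and the exclusion rule is too unclear to serve as one.
- **A contrast by dose or duration might be in an analysis plan that is not shown.** It might, and the Protocol does say that side effects depend on dose and time used. Such a contrast would still be between infants. No analysis plan can supply a comparison group or a start-of-infusion scan that was never planned.
- **No growth rate is given.** This stands. The percentages in step 3 are rejection probabilities at assumed values and do not show that growth of that size occurs. The identifiability result does not depend on them.
- **A start-of-infusion scan would not separate growth from drug.** Correct. Even a scan before the infusion raises the rank to 22 of 22 only if growth is taken as linear. The start scan serves the second problem, and rewording the aim serves the first.
- **An untreated group with the same disease is hardly feasible.** Accepted as an understandable limit. The point is then that the aim should match the design.

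**Conclusion.** The concern holds and should be fixed. The Protocol states a causal aim but fixes a design in which, within each infant, drug effect and growth enter only as a sum (rank 21 of 22). This rests on uninterrupted infusion, all scans on the drug and linear age and drug terms with a free intercept per infant. Between-infant contrasts are weak under the assumed spread of start ages (correlation 0.96 to 0.76) and open to confounding. The size of the bias from growth, and of the change missed before the first scan, cannot be stated from the document.

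**What to change.** 1. In the second bullet of Study Design, set the first of the weekly scans already planned at infusion start or as near to it as feasible, for example within 24 hours, without delaying the infusion. Record the time since infusion start at every scan, and flag infants who have no such scan.
2. Reword the aim and the planned conclusion to *change in pyloric wall thickness during PGE1 infusion*. State that, without an untreated comparison or age-specific reference values, the change is not attributed to PGE1. Adjustment for age and weight may be reported as exploratory, but it does not support attribution.

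The cost is small: the same number of scans, the same bedside device and one recorded time per scan. The drawbacks are a softer claim and some infants without a start-of-infusion scan, because treatment may begin at once while consent is still needed.

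### No reference scan is set before or at the start of PGE1, so change before the first scan is missed and the recorded increase can cover different stretches of exposure

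*Protocol*

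**What the plan says.** The aim, in the narrative under the protocol's title heading, is causal in wording: "we aimed to evaluate the effects of the drug on pyloric wall thickness prospectively with weekly ultrasonography measurements". The same section includes babies "who were receiving prostaglandin E1 infusion due to PDA-dependent congenital heart disease will be included in the study", with no limit on how long the infusion has already run.

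Under Study Design, the second bullet sets the whole measurement schedule: "Pyloric thicknesses will be measured by a pediatric radiologist once a week (at least twice) during the period when patients use PGE1". The third bullet gives the quantity analysed: "increases in the pyloric wall thickness dimensions will be compared with statistical analysis". The first bullet places inclusion after family consent, with no time limit relative to infusion start.

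The background paragraph says that PGE1 should begin at once when the diagnosis is confirmed, but links no scan to that moment. The target is 20 cases, set by expected admissions over 18 months. No SD, effect size or time course of thickening is given.

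**The concern.** An increase needs a starting point. For a drug effect with no comparison group, the natural one is thickness before or at the start of exposure. Here every scan is scheduled while the drug is running, and the interval from infusion start to first scan is left open. A protocol-compliant first scan may fall at the start or some days into treatment, and in the second case the reference may already be affected by the drug.

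Two things follow. Change before the first scan is lost. And the same recorded increase in two infants can stand for different parts of the exposure. The protocol itself says that PGE1 side effects in general depend on dose and duration of use, so exposure time matters on its own reasoning.

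This is not a detail that an analysis plan can supply later. A plan can model time since infusion start if the times were recorded, but it cannot recover an early scan that was never taken.

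**Working it through.** **Text check.** Four places could tie the first scan to infusion start.

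- Aim: weekly measurements in infants given PGE1; no start-of-infusion scan.
- Inclusion text: infants receiving PGE1; no limit on prior exposure.
- Background: prompt start of PGE1 on diagnosis; no scan mentioned.
- Study Design, second bullet: weekly, at least twice, during use; no day for the first or last scan.

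None fixes the interval. There is no figure in the plan to reproduce, because the 20 cases come from admissions and not from a power formula.

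**Stretch covered.** Inputs: scans every 7 days (protocol); infusion length D and lag d to the first scan (both assumed).

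Number of scans = floor((D − d)/7) + 1. Days covered = 7 × floor((D − d)/7), starting on day d.

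| D (days) | d = 0 | d = 3 |
|---|---|---|
| 14 | 3 scans, days 0–14, 14/14 = 100% | 2 scans, days 3–10, 7/14 = 50% |
| 21 | 4 scans, days 0–21, 21/21 = 100% | 3 scans, days 3–17, 14/21 = 67% |
| 28 | 5 scans, days 0–28, 28/28 = 100% | 4 scans, days 3–24, 21/28 = 75% |

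All six infants meet the two-scan minimum. Across a row, the lag changes what is covered. Down the d = 0 column, the span still runs from 14 to 28 days, so infusion length and number of scans matter as well as the lag.

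**First pair of scans.** With a first scan on day s and a second on day s + 7, exposure at the second scan is 7, 8 or 10 days for s = 0, 1 or 3. The overlap with the true first week is (7 − s)/7 = 100%, 86% or 57%. This needs an assumed lag but no assumed shape of thickening.

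**Illustration of direction.** For an assumed thickening curve f, ratio = [f(s + 7) − f(s)] / [f(7) − f(0)].

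- Linear: the ratio is 1 for every s.
- Plateau with half-time h: the ratio reduces to 2^(−s/h).
- Quadratic: (14s + 49)/49 = 1 + 2s/7.

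| Assumed shape | s = 0 | s = 1 | s = 3 | Mean, 20 lags evenly spaced over 0–3 days |
|---|---|---|---|---|
| Linear | 1.00 | 1.00 | 1.00 | 1.00 |
| Plateau, h = 7 days | 1.00 | 0.91 | 0.74 | 0.87 |
| Plateau, h = 3 days | 1.00 | 0.79 | 0.50 | 0.72 |
| Quadratic | 1.00 | 1.29 | 1.86 | 1.43 |

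Shapes, half-times and lags are all assumptions. They show that the effect can go either way or be absent; they estimate nothing about this trial.

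**The case against.** The best reply is that the lag is probably short. PGE1 is to start at once on diagnosis. Weekly scanning, read naturally, means that a full week of infusion without a scan departs from the schedule. An exclusion clause also refers to infants whose infusion is "discontinued by taking the second ultrasonographic measurement in the first week of life will be excluded from the study", which sets the early scans against the first days of life. This stands as a reason to expect lags of days, and it is why no lag of 7 days or more is used above. It does not close the gap: the clause counts age and not exposure, and none of these statements says when the first scan is due. The first Study Design bullet also speaks of infants who have to receive PGE1, which fits enrolment at the time treatment is indicated, but it sets no scan time either.

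A second reply is that unequal exposure has other causes. That is right. Infusion length and number of scans vary even if every first scan is on day 0, and a timing rule alone would not remove that. Hence the fix also asks for analysis by time since infusion start.

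A third is that no harm is shown. A reader might infer that first scans will be late, or that the study will understate the drug's effect. The document supports neither. It shows no long lag, and without a time course the sign of any bias is unknown. Under linear thickening the weekly change is unaffected.

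Finally, infusion and scan times may well be recorded on the data-collection form; nothing in the protocol says otherwise. But recorded times do not replace a missing early scan.

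**Conclusion.** The point holds in limited form. The protocol sets no reference scan before or at the start of PGE1 and describes no comparison group. Its measure of increase therefore omits whatever happened before the first scan and can cover different stretches of exposure. Variation in infusion length and number of scans contributes to the second problem.

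The absence of a timing rule rests on the text alone. The size does not: the range of 0.50 to 1.86 at a 3-day lag depends wholly on assumed shapes and includes no effect at all, and no loss of power can be derived. It would go too far to say that the results will be biased, or that first-scan timing alone makes exposure unequal. The change should be made because it is cheap and protects the study's central measurement, with medium confidence in how much it matters in practice.

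**What to change.** 1. State in the Study Design bullet that the first scan is done before PGE1 starts where feasible, and otherwise within a stated window after the start, without delaying or altering the infusion. The sponsor should choose the window; 24 to 48 hours is an example and an assumption, not a figure from the document.
2. Record the date and time of infusion start, including any start at a referring hospital, and of every scan.
3. Analyse thickness against time since infusion start in all infants, with those first scanned inside the window as a sensitivity analysis. The modelling detail can sit in the analysis plan.

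The cost is one sentence, a few data fields and earlier timing of a bedside scan that is already planned. No infant is dropped from the main analysis. The downside is that some early scans will be missed because consent is not yet given or the infusion starts out of hours. Those infants stay in the main analysis with their recorded lag, so some variation remains but it is known.

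### The protocol promises an undefined post-study observed power in place of a prior calculation; in its usual meaning this adds essentially nothing to the p-value and is not evidence on whether 20 infants were adequate

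*Protocol*

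**What the plan says.** All of this is in the Study Design section of the protocol.

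- **Sample size and comparison.** "After reaching the sufficient number of cases (20 cases), increases in the pyloric wall thickness dimensions will be compared with statistical analysis". No test, significance level, effect size or standard deviation is given.
- **Basis of the 20.** "The number of cases was determined in accordance with the rate of hospitalization in our unit during the determined period (18 months". This is a feasibility basis and is stated openly.
- **Power.** The reason given for having no prior calculation is the state of the literature: "since the studies are in the form of a case report and the original article cannot be found in the literature". The same sentence continues that "the observed power of the study will be calculated after the study is completed". The term is not defined, and no change in wall thickness is named for which power would be calculated.
- **Measurements.** Scans are taken "once a week (at least twice) during the period when patients use PGE1", so infants may contribute different numbers of scans.

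**The concern.** Sizing the study on admissions is not the problem. The problem is what is offered in place of a prior calculation. Observed power usually means power computed as if the observed effect were the true one. It then repeats what the p-value already says and carries no separate information on what 20 infants could have shown.

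The risk lies in interpretation. A non-significant result will tend to come with a low figure, which can be read as too few infants even if the confidence interval is narrow enough to rule out an important thickening. A clearly significant result will come with a higher figure, which can look like independent confirmation. The protocol says that no earlier study of this effect in newborns exists, so readers may lean on how this one is reported.

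**Working it through.** **Inputs.** From the protocol: n = 20, and at least two scans per infant. Not in the protocol, so assumed for illustration: a paired t-test of the within-infant change between two scans, two-sided, 5%. The figure of 20 has no statistical inputs, so there is no sample-size calculation to reproduce.

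**Step 1: observed power as a function of p.** With df = 19 the critical value is t(0.975, 19) = 2.093. For a result with two-sided p-value p, the observed statistic is t_obs = t(1 − p/2, 19). Observed power sets the noncentrality equal to t_obs:

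observed power = P(T > 2.093) + P(T < −2.093), where T is noncentral t with df 19 and noncentrality t_obs.

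| p | t_obs | Observed power |
|---|---|---|
| 0.01 | 2.861 | 77% |
| 0.05 | 2.093 | 51% |
| 0.10 | 1.729 | 38% |
| 0.20 | 1.328 | 24% |
| 0.50 | 0.688 | 10% |

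Only p, n and the significance level enter. Under this test every non-significant result shows at most about 51%.

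**Step 2: does it speak to sample size?** Repeating the calculation at p = 0.05 for n = 10, 20, 40 and 100 gives 52.4%, 51.1%, 50.5% and 50.2%. At p = 0.20 it stays between 23.6% and 24.8%. For a given p-value the figure hardly moves between 10 and 100 infants, so it cannot tell whether 20 was adequate.

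**Step 3: does it speak to precision?** The 95% confidence interval half-width for the mean change is 2.093/√20 = 0.468 SD of the change. If the SD doubles, the interval in mm doubles in width. At a given p-value, observed power is unchanged, because the SD does not appear in Step 1.

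**Step 4: other tests.** The protocol names no test, so the result was checked beyond the t-test, always at n = 20 and 5%.

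- *Balanced, spherical repeated-measures F-test with k scans* (df k − 1 and 19(k − 1), noncentrality (k − 1) × observed F). At p = 0.01, 0.05, 0.20 and 0.50, three scans give 80%, 58%, 33% and 16%, and four scans give 83%, 64%, 40% and 21%. The link with p is still exact, but the ceiling moves to about 58% or 64%.
- *F-test with a sphericity correction.* At p = 0.05 with three scans, observed power is 58%, 56% or 53% for epsilon of 1, 0.8 or 0.6. With four scans it is 64%, 61% or 57%. It now depends on epsilon as well as p.
- *Wilcoxon signed-rank test*, with power computed from the observed mean and SD and the usual 0.955 efficiency. In simulation with normal data, results with p between 0.045 and 0.055 had observed power of about 38% to 62% (5th to 95th percentile). Some non-significant results reached about 72%. With skewed data the corresponding figures were about 36% to 71%, and up to about 80%.

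The exact link and the fixed ceiling therefore belong to the first two tests in this working: the paired t-test and the balanced, spherical F-test. For the others the figure is largely driven by p but not fixed by it.

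**Step 5: is it a usable estimate of true power?** For the two-scan t-test, in simulation, observed power ranged from 7% to 97% (5th to 95th percentile) when true power was 50%, and from 23% to 99.8% when true power was 80%.

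**The case against.** The strongest reply has four parts.

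- **The meaning is inferred.** The term is undefined in what reads as a translated text, and it may mean power for a relevant change using the observed SD. That calculation would escape the criticism. This stands as far as it goes, but no such change is named, so the sentence needs correcting or clarifying on either reading.
- **The purpose is inferred.** A reader might infer that the protocol will use the figure to prove that 20 was enough. It does not say so. It calls 20 sufficient, explains why no prior calculation was possible, and offers the later figure in its place. That makes the use likely but does not state it.
- **The mathematics can be overstated.** A reader might also infer that observed power is a one-to-one function of p under any test, and that no non-significant result could ever exceed about 51%. The documents do not support this, because no test is named and scan numbers may differ between infants. Under a Wilcoxon test or a sphericity-corrected F-test the link is loose and the ceiling is not exact. This part of the objection stands in full.
- **The harm is small.** Observed power is not a decision rule, a stopping rule or a substitute for the main comparison. This also stands and sets the severity.

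It would be wrong to answer that the detail may sit in an unseen SAP. The observed-power calculation is a commitment written into the protocol, not something the protocol leaves open.

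**Conclusion.** The point holds, as a minor one. In its usual meaning the promised figure adds essentially nothing to the p-value and is not evidence on the adequacy of 20 infants. That conclusion does not depend on which common test is chosen. The numerical values do: the 51% ceiling rests on an assumed paired two-sided 5% t-test with 20 analysed infants and should be cited only as an illustration.

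The feasibility basis of the sample size is not criticised. No measurement, eligibility rule or patient is affected. What is at stake is how a null or positive result is read.

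**What to change.** Delete the observed-power sentence and replace it with wording such as: *The result, including the adequacy of 20 infants, will be interpreted by the estimated change in pyloric wall thickness between the scans chosen for the main comparison, with its 95% confidence interval.* Which scans those are can be settled in the protocol or the SAP.

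Alternatively, if power for a relevant change was intended, say so and name that change in mm before the data are seen. Power for it would then be calculated with the observed SD of the change.

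The cost is one sentence. The number of infants, the scans and the eligibility rules stay as they are. The downside is that the sample-size justification looks less favourable, since it then rests openly on feasibility alone. What 20 infants can show could be stated in advance only in SD units (a half-width of about 0.47 SD of the change under the paired assumption), because the protocol gives no SD.
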